8.7 Concomitant Interventions (treatments)

All participants receive standard of care treatment for *S. aureus* bacteraemia as clinically indicated and according to local and international recommendations. This includes targeted antibiotic treatment for at least 2 to 6 weeks, mostly applied intravenously. The choice of standard of care antibiotic will not be affected by the study. In case clindamycin is administered after enrolment, this must be documented in the eCRF.

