Methicillin-susceptible *S. aureus* (MSSA) represents 95% of *S. aureus* antibiotic resistance profiles in Switzerland.² The standard management of MSSA bacteraemia consists of an intravenous treatment with an anti-staphylococcal beta-lactam antibiotic such as flucloxacillin or cefazolin for 2-6 weeks and rapid source control if possible.²⁶⁻²⁹ Previous studies attempted to increase the antimicrobial efficacy of standard therapy by adding a second antibiotic with evidence of additive or synergistic killing capacity *in vitro*. As identified by a recent systematic review,³⁰ gentamicin,³¹⁻³³ rifampicin,^{34,35} levofloxacin,³⁶ daptomycin,³⁷ or fosfomycin³⁸ have been added to standard antibiotics in RCT of bacteraemia with methicillin-susceptible *S. aureus* (Table 2). Unfortunately, none of these RCTs succeeded in demonstrating a significant improvement in clinical outcomes. Several factors may have contributed to the shortcomings of these clinical trials. One possible factor is that the interventions may not have effectively addressed the underlying pathophysiologic factors responsible for the poor outcomes in patients with *S. aureus* bacteraemia. Limitations of the RCTs also include that the sample sizes were generally small, making it difficult to detect small, but relevant differences in mortality. In addition, these RCTs did not prioritise the assessment of other important patient-related outcomes, such as post-infection functional status.

Study (year)	RCT design sample size	Population	intervention	Control	PROM	Primary outcomes
Abrams (1979) ²⁵	open-label single-centre N=35	S. aureus endocarditis in intravenous drug users	Standard + gentamicin	Standard (Beta-lactam)	no	time to defervescence: I: 6.3 days vs. C: 6.6 days mortality/relapse of infection I: 0%, vs. C: 0% No difference in primary outcome
Korzeniowski (1982) ²⁶	open-label multicentre n=78	S. aureus endocarditis in drug-addicts and non-addicts	Standard + gentamicin	Standard (nafcillin)	no	cure: I: 60% vs. 65% No difference in primary outcome
Van der Auwera (1985) ²⁸	double-blind placebo-controlled multicentre n=29 (bacteraemia)	S. aureus infections (subgroup with bacteraemia)	Standard + rifampicin	Standard (oxacillin / vancomycin) + placebo	no	clinical cure: I: 69%, C: 63% No difference in primary outcome

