3.4 Clinical Evidence to Date

Linezolid is an established antibiotic treatment option for skin- and soft tissue infections as well as for pneumonia, especially in case of MRSA due to the low rate of linezolid resistance.⁶⁰ Detailed information on pivotal studies of linezolid can be found in the SMPC. For nosocomial MRSA pneumonia, linezolid has been shown to be superior to the commonly administered intravenous vancomycin.⁵⁹ For MRSA bacteraemia, linezolid is a safe and effective alternative to standard-of-care glycopeptide (vancomycin/ teicoplanin).⁶¹⁻⁶³ A trial directly comparing standard-of-care beta-lactam therapy with linezolid in MSSA bacteraemia is lacking, since beta-lactam therapy is regarded as most effective for MSSA. Limited clinical data exist regarding combination therapy with linezolid in *S. aureus* bacteraemia. Two observational cohort studies (involving a total of 54 linezolid treated participants) reported favourable outcomes (microbiological response, success rate, mortality) with salvage combination therapy using linezolid and a carbapenem.⁶⁴⁻⁶⁵ Successful treatment was also observed in a case of MRSA bacteraemia and meningitis with linezolid, daptomycin, and rifampicin.⁶⁶ Linezolid may be most effective when started as early as possible according to the open label RCT by Wilkox et al.⁶⁷ Even though the study was underpowered, it supports the hypothesis that empirically initiated linezolid might result in better survival. Similarly, a prospective observational single-centre study found significantly improved survival in participants with MRSA bacteraemia empirically receiving linezolid compared to a glycopeptide (adjusted odds ratio for survival 7.7; 95%CI 1.1–53).⁶⁸

The potential clinical impact of toxin inhibition by linezolid is demonstrated in a case report on the successful treatment of a staphylococcal toxic shock syndrome.⁶⁹ In addition, a review of 93 cases of *S. aureus* necrotizing pneumonia revealed reduced mortality rates when antibiotic therapy incorporated an anti-toxin agent, such as clindamycin or linezolid.⁷⁰ Our systematic search showed that no RCT has assessed the effect of adding linezolid to the standard antibiotic therapy in patients having *S. aureus* bacteraemia.

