6.4 Unblinding Procedures (Code break)

The study medication (10 tablets per container) with a unique randomisation number will be distributed to the study centres. For each unique randomisation number, the study centre will receive a sealed opaque envelope with the information if the container contains linezolid or placebo. The treating physician will only be allowed to open an envelope if safety concerns require knowing a participant's allocated intervention. All unblinding procedures must be entered within the eCRF. The envelopes will be checked during monitoring visits and after the completion of the study.

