7. STUDY POPULATION

7.1 Eligibility criteria

Inclusion criteria:

- *S. aureus* grown from at least one blood culture
- Hospitalised at a participating centre
- ≥ 18 years old
- Written informed consent or fulfilling criteria for an emergency exception from informed consent requirements

Exclusion criteria:

- Administration of the initial drug treatment not feasible within 72 hours since the collection of the first positive blood culture with *S. aureus*
- Documented history of positive blood cultures for *S. aureus* occurring between 72 hours and 180 days prior to the eligibility assessment
- Necrotising fasciitis
- Currently receiving linezolid or clindamycin
- Use of any monoamine oxidase A or B inhibitor within the last two weeks
- Known hypersensitivity to linezolid or any other ingredients of the study drugs
- Current severe thrombocytopenia (i.e. $<30 \times 10^9/l$)
- Oral application of study drug not possible (per mouth or per gastric tube)
- Currently breastfeeding
- Local treating team believes that death is imminent and inevitable
- Patient is receiving end of life care and antibiotic treatment is not considered appropriate
- Local treating team believes that participation in the study is not in the best interest of the patient
- Any indication that the patient is unwilling to participate in the study including an advance directive stating such unwillingness

General:

Patients taking serotonergic drugs such as selective serotonin reuptake inhibitors (SSRI) or tricyclic antidepressants are not generally excluded. See detailed information on risk assessment and precautions in chapter 8.6 *Trial specific preventive measures*.

Pregnant women will not be excluded from study participation per se, as linezolid is not formally contraindicated during pregnancy. Limited data exist on the treatment of pregnant women with linezolid, mainly from clinical trials in treating multidrug-resistant tuberculosis. In 31 pregnancies under linezolid exposure, none reported foetal toxicity.⁹⁵ In the event of pregnancy, the treating physician and the patient (or the patient's next of kin) will assess whether the potential benefits outweigh the potential risks to the foetus.

Linezolid has been shown to pass into breast milk and accordingly, breastfeeding should be discontinued prior to and throughout administration of linezolid.

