8.3 Dose modifications

Drug-related AEs leading to discontinuation of the drug are expected to be extremely rare when linezolid is used for 5 days. Discontinuation of IMP may occur in the situations listed in chapter 6.4 *Unblinding Procedures (Code*

break) and chapter 7.4 *Criteria for withdrawal / discontinuation of participants*. The study medication will be given twice a day for 5 days (in total 10 administrations) with approx. 12 hours interval between each administration. If maintaining a fixed 12-hour interval is challenging due to the start time (e.g. if subsequent doses would need to be administered in the middle of the night), the treating physician may adjust the first dosing interval according to standard practice. However, the interval should not be shortened or extended by more than 6 hours. Further dose modifications are not allowed.

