11.4 Planned Analyses

11.4.1 Datasets to be analysed, analysis populations

Analyses will be performed on the full analysis set (i.e., all randomised participants) and the per protocol dataset

(i.e., those who received at least 7 out of 10 doses of linezolid or placebo). The primary estimand to be calculated in this study is the effect (summarised as the win ratio) of being randomly assigned to treatment with linezolid in the patient population (i.e., equivalent to an intention-to-treat analysis). We will also estimate the treatment effect among the treated participants (i.e., the per protocol dataset).

A detailed analysis plan will be written before closing the study database. Of note, we are currently conducting a systematic scoping review, assessing current practices how to analyse a hierarchical composite outcome. These results will inform our pre-specified analysis plan. Furthermore, we will consider further developments in risk-score classifications for *S. aureus* bacteraemia (e.g. for a potential use of a matched win-ratio versus unmatched win-ratio). The statistical analysis plan will be made publicly available (on clinicaltrials.gov). Currently we intend to conduct the following analyses:

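### Section 8.7 names only clindamycin for specific documentation after enrolment: no rule covers open-label linezolid, and the per-protocol set would not detect it

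*Protocol*

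**What the plan says.** Protocol section 7.1 lists among the exclusions: "Currently receiving linezolid or clindamycin". The criterion applies at the eligibility assessment only.

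For the period after enrolment, section 8.7 asks for standard care as clinically indicated and in line with recommendations, and states: "The choice of standard of care antibiotic will not be affected by the study". It then adds the one agent-specific instruction: "In case clindamycin is administered after enrolment, this must be documented in the eCRF". Linezolid is not mentioned there.

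The protocol itself describes clinical uses of linezolid in this disease. Section 3.4 says: "For MRSA bacteraemia, linezolid is a safe and effective alternative to standard-of-care glycopeptide". Sections 3.4 and 3.5 also describe salvage combination use and the oral route, and section 2.2 mentions oral continuation after intravenous treatment.

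On the blind, section 6.4 says: "The treating physician will only be allowed to open an envelope if safety concerns require knowing a participant's allocated intervention". On analysis, section 11.4.1 defines the per-protocol dataset as "those who received at least 7 out of 10 doses of linezolid or placebo". The adherence check in section 11.4.4 uses the same count of doses.

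**The concern.** The entry criterion treats linezolid and clindamycin as equally incompatible with the comparison. Once a participant is enrolled, only clindamycin is singled out, and the investigational drug itself is not. A treating team that follows 8.7 may prescribe linezolid openly while blinded study drug continues, and the protocol does not say what then happens to the study drug.

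Two things are at stake. In the linezolid arm, total exposure could exceed the five-day course on which sections 3.7, 3.9 and 8.6 base their expectation of low toxicity. In the placebo arm, early open-label linezolid is a crossover: it pulls the intention-to-treat comparison towards no effect, and it leaves the per-protocol analysis, which is meant to estimate the effect among the treated, with a control who received the test drug.

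**Working it through.** **Step 1. Rules side by side.**

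| Question | Clindamycin | Open-label linezolid |
|---|---|---|
| Excluded if current at entry (7.1) | Yes | Yes |
| Restricted after enrolment (8.7) | No | No |
| Named for eCRF documentation after enrolment (8.7) | Yes | No |
| Rule for blinded study drug if prescribed | None | None |
| Affects per-protocol membership (11.4.1) | No | No |

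**Step 2. What general capture would show.** The synopsis (Measurements and procedures) says that concomitant treatments, including the standard antibiotic, are taken from medical records. The schedule in 9.1 has a row for antibiotic or surgical treatment at day 90. Section 9.2.2 records the number of antibiotic days at discharge, with a further check at day 90. Section 9.2.1 assesses treatment changes at day 90. Open-label linezolid could therefore appear in the data. None of these items identifies it by name or requires its timing against days 1 to 5, so overlap with study drug is not assured of being recoverable.

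**Step 3. Per-protocol consequence.** Take a placebo participant with 10 of 10 study doses and open-label linezolid from day 2. Since 10 is at least 7, the participant stays in the per-protocol set as an adherent control. The adherence check in 11.4.4 would also count the participant as adherent.

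**Step 4. How many might be affected.** Section 3.1 says that methicillin-susceptible isolates ("MSSA) represents 95% of" Swiss *S. aureus* resistance profiles) predominate, which leaves about 5% MRSA. If that share applied here:
- whole trial: 0.05 × 606 = 30.3, about 30 participants;
- placebo arm: 0.05 × 303 = 15.2, about 15 participants.

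This counts participants with the indication for which 3.4 calls linezolid an alternative. It is not a forecast of use, and the protocol gives none.

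**Step 5. Power, illustrative only.** Assume that a fraction c of the placebo arm crosses over early and gains the full effect, that the effect shrinks by the factor (1 − c), and that the standard error is unchanged. At 90% power and two-sided 5%, the standardised effect is 1.96 + 1.28 = 3.24. Power is then Φ(3.24 × (1 − c) − 1.96):
- c = 2%: Φ(3.175 − 1.96) = Φ(1.215) = 0.89
- c = 5%: Φ(3.078 − 1.96) = Φ(1.118) = 0.87
- c = 10%: Φ(2.916 − 1.96) = Φ(0.956) = 0.83

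As a cross-check, the unmatched win ratio was simulated with 275 per arm and the event and missing-data rates of section 11.2. The plan's 550 cannot be reproduced exactly, because the log-normal length-of-stay parameters are not given. The simulation assumed a median stay of 16 days, a log-SD of 1.0, a rise of 0.5 in log stay with a complication, and a log-mean multiplied by 0.8 under linezolid. This was the setting nearest 90% power. Over 1,000 datasets:

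| Early placebo crossover | Power | Win ratio |
|---|---|---|
| 0% | 93% | 1.43 |
| 2% | 92% | 1.41 |
| 5% | 91% | 1.41 |
| 10% | 86% | 1.37 |
| 20% | 77% | 1.33 |

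Monte Carlo error is about 1 point. With a log-SD of 0.6 and a shift of log(0.8), power starts at only 74% and falls to 69% at 5% crossover. That setting is well below the planned 90%, so it is not used for the headline figure.

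**The case against.** The strongest reply is that this is a pragmatic trial. An entry criterion need not continue as a prohibition, and the intention-to-treat estimand in 11.4.1 already keeps these participants as randomised. That is right: the primary analysis needs no change. Refinement of the per-protocol set could also be left to an analysis plan. But the protocol already fixes that set by dose count, and no later plan can recover timing that was not collected.

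Most foreseeable use would also fall late. Oral continuation follows intravenous treatment, and salvage follows persistent infection. Section 3.5 expects the greatest benefit in the first three days, so late linezolid is hardly a crossover to the tested strategy. This stands, and it limits the concern about bias to the intervention phase.

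On safety, the care team is told of participation (9.3.2), infectious disease specialists who are local investigators are routinely involved (3.8), and the code can be broken for safety. So the team would know that combined exposure is possible, though not whether it is occurring. Monitoring also continues after day 7: kidney injury to day 14, *C. difficile* and serious events to day 90.

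Two stronger readings are tempting, and the text supports neither. A reader might infer that clindamycin is the only antibiotic that has to be documented; the general capture in step 2 shows otherwise. A reader might also infer a contradiction with section 8.3, where "Further dose modifications are not allowed" appears. That sentence closes a paragraph on the timing of study medication and does not govern background antibiotics.

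**Conclusion.** The gap is real and narrow. Section 8.7 names clindamycin but not the investigational drug. No section says how open-label linezolid after enrolment is flagged and dated, or how blinded study drug is handled if it is prescribed. The per-protocol definition would retain an early placebo crossover as an adherent control.

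The effect on power is an assumption, not a finding. It is about 2 to 3 points at 5% early placebo crossover, from settings that start near 90%, and less if use is rarer or later. On the Swiss MRSA share, 5% would require about all 15 expected placebo participants with MRSA to receive linezolid early and gain the full effect. The 10% and 20% rows have no source in the protocol and only show the slope. A reader might infer from them that the primary analysis is at serious risk, and the documents do not support that. The reasons to act are the possibility of combined exposure without a rule and a crossover that the per-protocol set cannot see. The change should be made, but the trial does not depend on it.

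**What to change.** 1. In section 8.7, name linezolid beside clindamycin and require start and stop dates in the eCRF, so that overlap with study drug can be established.
2. Reconcile 7.1 and 8.7 so that the protocol states how blinded study drug is handled when the treating team wants open-label linezolid. Which clinical rule applies is for the sponsor to set.
3. Amend the per-protocol definition in 11.4.1 so that it accounts for open-label linezolid during the intervention phase, and report such use by arm. The intention-to-treat analysis stays as it is.

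The cost is one eCRF item, a short amendment and a slightly smaller per-protocol set. No visits or participants are added. The item should be in place while participants are being treated, because it depends on prospective dates.

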8.8 Study Drug Accountability

Study drugs will be accurately and adequately monitored from shipment to the site until return or disposal. Dates of receipt/expiry/use/return will be recorded.

8.9 Return or Destruction of Study Drug

Study sites will destroy the left-over study medication according to site-specific SOP. In the rare cases that participants are discharged from the hospital before completing the study medication, they will be provided with the necessary tablets to continue their treatment at home until the 5-day course is completed. They will be instructed to return any unused tablets (e.g., if they are unable to take a dose for any reason) to a pharmacy for proper disposal.

9. STUDY ASSESSMENTS

9.1 Study flow chart/ table of study procedures and assessments

Study Schedule

	Screening	Enrolment	Intervention phase					In-Hospital Follow-Up (applicable only if participant remains hospitalised)				Close-out
Time point	0-72h before randomisation		Day 1	Day 2	Day 3	Day 4	Day 5	Day 7	Day 14	Day 28	Discharge day	Day 90
S. aureus positive blood culture	X											
Identification of patient		X										
Eligibility checks		X										
Informed consent		X										
Randomisation			X									
IMP administration			X	X	X	X	X					
Time point	0-72h before randomisation		Day 1 (-1 day)	Day 2	Day 3 (±1 day)	Day 4	Day 5 (±1 day)	Day 7 (±1 day)	Day 14 (±3 days)	Day 28 (±4 days)	Discharge day	Day 90 (±7 days)
Clinical assessments												
Baseline data			X ¹									
SIRS criteria								X				
All-cause mortality								Assessed until day 90				
Clinical failure										X	X	X
Length of hospital stay											X	
Length of ICU stay											X	
Antibiotic and/or surgical treatment												X
Laboratory assessments												
Blood cultures				X			X ²					
Creatinine			X				X			X ³		
CRP			X				X					
ALT and gGT			X				X			X ³		
Blood count (Hb, Tc, Lc)			X		X		X	X				
Linezolid trough conc.							X ⁴					
Microbiological failure										X	X	X
New antibiotic resistance												X
Patient reported outcomes												
Quality of life (SF-36)												X
Return to usual level of function												X
Safety assessments												
Serotonin toxicity, myelosuppression, hyperlactataemia ⁵			X	X	X	X	X	X				
Acute kidney injury ⁵							X		X			
C. difficile-associated diarrhoea ⁵												X
SAE / SAR			Collected until day 90									

Abbreviations: S. aureus – *Staphylococcus aureus*; SAE – Severe Adverse Event; SAR – Severe Adverse Reaction; SIRS - Systemic Inflammatory Response Syndrome; ICU – Intensive Care Unit; CRP – C-Reactive Protein; ALT – Alanine Transaminase; gGT – Gamma-glutamyl Transferase; Hb – Haemoglobin; Tc – Thrombocytes; Lc – Leukocytes; SF-36 – Short Form-36

¹ Baseline data include: date of hospital admission, index blood culture, linezolid susceptibility, ethnicity, vital signs, comorbidities, standard antibiotic treatment, markers of severity (mechanical ventilation, cardiac arrest, use of vasopressors, ICU), injection drug use, mental health diagnosis.

² Assessment of persistent bacteraemia. Only required if day 2 blood culture is positive or recorded if done as part of standard of care.

³ Choose the result that represents the highest level recorded between day 6-14.

⁴ Linezolid trough concentration is only measured in a subset of participants in participating centres.

⁵ Adverse events of special interest until day 7 include: serotonin toxicity, myelosuppression, hyperlactataemia; until day 14: acute kidney injury; until day 90: C. difficile-associated diarrhoea.

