Acute kidney injury according to the modified Kidney Disease Improving Global Outcomes (KDIGO) stage 1 is defined as an increase in serum creatinine of $\geq 26.5 \mu\text{mol/L}$ from randomisation (baseline) to study day 5 or an increase in serum creatinine by 1.5 times or more the level of randomisation within 14 days of

randomisation. To collect this outcome, the serum creatinine at baseline (on randomisation day 1 or the calendar day prior to randomisation), day 5 (± 1 day), and only if participant remains hospitalised, at day 14 (± 3 days) will be documented in the eCRF. The values will be captured from available data in the hospital information system or from the participant's primary care physician, respectively.

- *C. difficile*-associated diarrhoea within 90 days.

The treating clinicians will assess for *C. difficile* infection based on the centre-specific diagnostic algorithm if clinical suspicion arises due to diarrhoea during antibiotic treatment. *C. difficile* infection will be evaluated on day 14, at discharge, and on day 90 by reviewing the participant's electronic health records. If a participant reports severe diarrhoea during a 90-day follow-up phone call, occurring after discharge and managed outside the centre, the responsible physician may be contacted to determine if a *C. difficile* infection was diagnosed.

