9.3.6 Assessment of routine laboratory measurements (day 1-7)

Laboratory assessments at start and during treatment will be part of the clinical routine. Either on the day before or on the day of study treatment start, participants will receive routine blood sampling which includes blood count (Hb, Tc, Lc), measurement of renal function (creatinine) and liver function (ALT, gGT), as well as inflammatory parameter (CRP). The study team will review the blood samples at start and during treatment and will re-order any missing laboratory measurements from the collected blood samples if, in rare cases, the necessary measurements for the study according to the visit plan were not routinely performed. No additional blood should be drawn to assess clinical routine measurements. The blood count should be measured 4 times between day 1 (-1) and day 7 (± 1), creatinine and CRP at least on day 1 and day 5 (± 1), creatinine also on day 14 (± 3) if a participant is still hospitalised.

9.3.7 Subproject *Molecular mechanisms of S. aureus bacteraemia* (day 1 until 48h after the patient's first negative blood culture)

Only for a subgroup of patients included in Basel, Switzerland.

Blood will be used to determine the location of *S. aureus* in the blood (intra- or extracellular).

For this, a maximum of one additional 7.5 ml EDTA tube of blood per day will be collected from day 1 until follow-up blood cultures remain negative for 48 hours.

- For patients who consented to further analysis of *S. aureus* in their blood, blood samples will be collected daily. If no routine blood work is performed on an eligible day, an additional blood draw should be performed to collect the sample.
- For patients enrolled via the confirmation of an independent physician under emergency exception from informed consent requirements, blood samples will only be collected during routine blood drawing.
- For patients who refused consent to further analysis in the blood, no additional blood samples for the subproject will be taken.

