- Laboratory signs of myelosuppression until day 7: Participants will be monitored for signs of myelosuppression (thrombocytopenia, anaemia, leukopenia) as part of the clinical routine blood sampling. If blood count shows signs of myelosuppression, the local investigator will be involved to assess the potential causality between the IMP and the laboratory measurements. The local investigator will then decide if the participant needs to stop the intervention.
- Evidence of hyperlactatemia until day 7: In case of a clinical suspicion of hyperlactatemia, the local investigators must collect a blood sample to assess if the lactate level is above the upper norm according to specific laboratory-defined reference ranges. For increased lactate levels, the causality with the study treatment will be assessed. The local investigator will then decide if the participant needs to stop the intervention.
- Acute kidney injury: the kidney function is measured in the blood (creatinine) regularly as part of the clinical routine. To collect this outcome, the serum creatinine at baseline, on day 5 (± 1), and only if participant remains hospitalised, at day 14 (± 3 days) will be documented. The values will be captured from available data from the hospital information system.
- *C. difficile*-associated diarrhoea within 90 days: The treating clinicians will assess for *C. difficile* infection based on the centre-specific diagnostic algorithm if clinical suspicion arises due to diarrhoea during antibiotic treatment. *C. difficile* infection will be evaluated on day 14, at discharge, and on day 90 by reviewing the participant's electronic health records. If a participant reports severe diarrhoea during a 90-day follow-up phone call, occurring after discharge and managed outside the centre, the responsible physician may be contacted to determine if a *C. difficile* infection was diagnosed.

9.3.12 Assessment of serious adverse events and serious adverse reactions (from enrolment until discharge, and at day 90 ±7)

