11.4.5 Safety analysis

The following adverse events and safety outcomes will be analysed descriptively by study group:

- Serious adverse reactions or serious adverse events in the 90 days following study entry
- The following adverse events of special interest until 14 days after study entry during the index hospital stay:
 - Clinical signs compatible with serotonin syndrome
 - Laboratory signs of haematotoxicity
- Acute kidney injury defined using modified Kidney Disease Improving Global Outcomes (KDIGO) criteria, modified according to SNAP trial:
 - Increase in serum creatinine by 26.5 µmol/l or more at any time from baseline entry to day 5

OR

- Increase in serum creatinine by 1.5 times or more the level at study entry (baseline) within 14 days of study entry
- *Clostridioides difficile*-associated diarrhoea

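### Acute kidney injury is defined on creatinine at any time to day 5 and within 14 days, but the protocol gives conflicting rules for the later value and asks for no peak up to day 5

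*Protocol*

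**What the plan says.** Five places in the protocol bear on this outcome.

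- **Section 11.4.5 (analysis).** The first criterion is a creatinine rise of 26.5 µmol/l "or more at any time from baseline entry to day 5". The second is: "Increase in serum creatinine by 1.5 times or more the level at study entry (baseline) within 14 days of study entry".
- **Section 9.2.4.1 (assessment).** The same thresholds appear, but the first criterion is a rise "from randomisation (baseline) to study day 5 or an increase in serum creatinine by 1.5 times or more", without the any-time wording. The values to be documented are baseline, day 5 (±1) "and only if participant remains hospitalised, at day 14" (±3).
- **Section 9.3.11.** The same three values are repeated: "To collect this outcome, the serum creatinine at baseline, on day 5" (±1), and day 14 (±3) if still hospitalised.
- **Section 9.3.6.** This sets what must be measured: "creatinine and CRP at least on day 1 and day 5" (±1), plus creatinine on day 14 (±3) for those still in hospital.
- **Section 9.1, schedule footnotes.** Footnote 3, attached to creatinine and to the liver enzymes, says "Choose the result that represents the highest level recorded between day 6-14". Footnote 5 sets the ascertainment period as "until day 14: acute kidney injury".

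**The concern.** An outcome defined by whether a threshold was crossed at any time in an interval needs the highest value in that interval, or all of the values. Two single values give that only for episodes that happen to be present on the sampling day. Here the documents also disagree on the later value: it is one result near day 14 in the text and the peak of days 6-14 in the footnote. An analysis plan cannot settle this afterwards, because it cannot recover values that were never entered.

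Acute kidney injury is a prespecified adverse event of special interest, and section 3.9 names raised creatinine and rare renal failure among the reported effects of linezolid. The DSMB sees safety summaries after 50 and after 200 participants (11.4.4). The collection rule therefore matters early.

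**Working it through.** The protocol gives no rate or time course for acute kidney injury, so there is no planned figure to reproduce. The check compares the days on which the definition can be met with the days on which a value can be recorded.

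**Days covered.** Randomisation is day 1 (Synopsis), so a rise can first be seen on day 2. The definition can be met on days 2-14, which is 13 days.

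| Rule | Days from which a value may come | Days never covered |
|---|---|---|
| Text (9.2.4.1, 9.3.11) | one from days 4-6, one from days 11-17 | 2, 3, 7, 8, 9, 10 (6 of 13) |
| Footnote 3 for the later value | one from days 4-6, peak of days 6-14 | 2, 3 (2 of 13) |

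**Window against limit.** Day 14 ± 3 is days 11-17. Days 16 and 17 lie beyond 14 days however day 1 is counted. Day 15 is also beyond footnote 5.

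**Illustrative capture.** Assumptions, none of them from the protocol:

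- Onset is equally likely on each of days 2-14.
- Creatinine stays above the threshold for L consecutive days.
- The participant stays in hospital and has a creatinine result every day.
- The two criteria are not modelled separately.

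Capture is the number of onset days for which the episode includes a recorded day, divided by 13. Sampling is on the nominal days.

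| L (days) | Text: days 5 and 14 | Footnote: day 5 and all of days 6-14 |
|---|---|---|
| 2 | 4/13 = 31% | 11/13 = 85% |
| 3 | 6/13 = 46% | 12/13 = 92% |
| 5 | 9/13 = 69% | 13/13 = 100% |
| 7 | 11/13 = 85% | 13/13 = 100% |

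For example, with L = 3 the text captures onsets on days 3, 4, 5, 12, 13 and 14. The footnote misses only onset on day 2, an episode lasting days 2-4. If sampling is instead spread evenly over the allowed windows, the text misses 76%, 64%, 47% and 40%, so it captures 24%, 36%, 53% and 60%. The footnote results remain 85%, 92%, 100% and 100%.

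**Effect on the comparison.** If both arms have the same capture c and there are no false cases, the observed difference is c × (p1 − p0), while the observed ratio is (c × p1)/(c × p0) = p1/p0. With an assumed true excess of 4 percentage points and L = 3, the observed excess is 0.46 × 4 ≈ 1.8 points under the text and 0.92 × 4 ≈ 3.7 under the footnote.

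**The case against.** The strongest reply is that the passages can be read together: the text names the assessment point and footnote 3 says which result to enter for it. On that reading the later value is already a peak and the gap on days 7-10 disappears. This is a fair reading, but 9.2.4.1 and 9.3.11 neither state it nor refer to the footnote. It also leaves the interval up to day 5 with one value, against an any-time criterion.

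Some stronger inferences are tempting and are not supported.

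- **That most short episodes will be lost.** This follows only if footnote 3 is ignored. The right-hand column above is just as consistent with the documents.
- **That 9.3.6 limits what is recorded.** It sets a minimum for testing and does not restrict documentation.
- **That the drug will look safer.** Participants, physicians and assessors are blinded, and randomisation is stratified by centre. Under-capture lowers counts in both arms. It shrinks an absolute difference but does not by itself move the ratio.
- **That values from days 15-17 create false cases.** The definition stops at 14 days, so applied as written they would not qualify. The practical result is a late value that cannot be used.
- **That sites will certainly diverge.** All sites use one eCRF with entry guidance, and its creatinine field is not visible in the protocol. Divergence is a risk, not an established fact.

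The consequences are also bounded. The outcome is analysed descriptively, with no alpha or power attached. Kidney injury that meets the SAE criteria is collected to day 90, and any adverse event leading to study drug discontinuation is captured separately.

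**Conclusion.** The point stands as a mismatch between definition and collection. The later value has two rules, its window overruns the 14-day limit, and no passage asks for the peak up to day 5. The first criterion of 11.4.5 therefore cannot be fully evaluated from the values the text requires. What can be missed is short, non-serious early episodes under either rule, plus episodes on days 7-10 if the text governs.

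The size depends on which rule governs: for episodes of 2 to 7 days, nominal-day capture runs from about 31% to 85% under the text and from about 85% to 100% under the footnote. Both ranges rest on assumed onset and duration and on daily results being available, so they show direction and spread rather than an estimate. The mismatch itself needs none of those assumptions. The effect is a diluted absolute difference in a descriptive safety outcome, and counts that may depend on how a site reads the rule. It does not touch the primary analysis, and it is worth correcting because the correction is cheap.

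**What to change.** State one rule in 9.1 (footnote 3), 9.2.4.1, 9.3.11, 11.4.5 and the eCRF:

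- Record the highest available routine creatinine from after baseline to day 5.
- Record the highest available routine creatinine from day 6 to day 14.
- Do not count values after day 14 toward acute kidney injury.
- Use the same any-time wording for the first criterion in 9.2.4.1 as in 11.4.5.

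Keep the day-5 (±1) and day-14 (±3) measurements in 9.3.6 as the minimum testing requirement. The day-14 measurement is the only creatinine that 9.3.6 requires after day 5. Without it the later peak would rest entirely on local sampling habits.

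The cost is wording and the eCRF fields. The values are already in routine hospital records and no extra blood is needed. The downside is that a peak depends partly on how often a ward samples, and section 9.3.12 notes that evaluation is much more frequent on the ICU. Stratification by ICU status helps to balance this between arms, but absolute rates should be read with it in mind.
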